**Protocol Title:**

A Multicenter, Randomized, Double-Blind, Placebo-Controlled, Multiple Dose Study to Evaluate Safety, Tolerability and Efficacy of Orally Administered ENT-01 for the Treatment of Parkinson's Disease-Related Constipation (KARMET)

Sponsor

Enterin, Inc.
[name]
[name]

Investigational Product
ENT-01**Study Phase**
2b**Protocol Number**
ENT-01-030**Clinical Trial Registry Number**
NCT Number: 03781791**IND NUMBER**
130770**Protocol Version Number**
Version 7.0**Protocol Version Date**
27April2021

Original Protocol: 21August2018
Amendment 1: 31December2018
Amendment: 15March2019
Amendment version #5: 8October2019
Amendment version #6: 11Dec2019

STUDY NUMBER ENT-01-030
AMENDMENT NUMBER 7

SUMMARY OF CHANGES

Section Number	Summary of Changes	Rationale for Change
Section 4.0, Study Synopsis	“80 subjects” changed to “up to 80 subjects”	To correspond with “60 evaluable subjects”
Section 4.0 Study Synopsis	“20 centers” changed to “25 centers”	Slow recruitment during Covid
Section 5.3 Study Synopsis	Requirement to take OTC laxatives for 6 weeks prior to inclusion removed; duration of constipation required changed to approximately 6 months	Unnecessary; subjects with more than 3 CSBMs per week do not proceed to randomization anyway.
Study Synopsis	Discontinuation of clonazepam removed	Sleep no longer being assessed
Section 5.4, 5.7 Study Synopsis	Discontinuation of pimavanserin removed	Subjects reluctant to participate and PIs feel it is an unnecessary exclusion
Section 6.2 Packaging and Labeling	Picture of actual label inserted to replace the previous picture	Provides a picture of the actual label and removable panel.
Section 6.3 Storage, Dispensing and Reconciliation of Study Drug and Identity of Investigational Products	Inserted “Controlled room temperature” as the storage temperature requirement. A definition of Controlled room temperature is also provided.	Allows for the minor temperature excursions outside the 20 - 25°C temperature range often experienced in the storage of IP at hospitals, pharmacies and clinical sites.
Section 8.2 – NCI- CTCAE Table	Definitions of Dose Limiting Adverse Events - Vomiting	Language was confusing to coordinators. More precise wording
Section 8.10	Reporting of Adverse Events (AEs) or Serious Adverse Events (SAEs) – AE’s and SAE’s begins after obtaining of informed consent	To clarify the inconsistency within the Protocol
Section 9.2.5 Study Synopsis	Sample size assumptions reworded to include standard deviation and 10% drop out rate assumption; sample size unchanged	More precise wording
Section 9.2.6 Study Synopsis	Data cut will be performed at 40 subjects changed to data cut may be performed at 40 subjects	To correspond to SAP
Study Synopsis Section 9.2.6	Mentioned that we performed an interim analysis earlier	Also mentioned in earlier amendment

Section 4.0, 4.1,4.2,4.3,4.5,4.6	Visit window broadened	Was too narrow; was leading to many, unnecessary minor protocol deviations
Section 4.1	Specifying that SAPS-PD and hallucination interview only need to be remeasured if hallucinations were present at baseline	Eliminating unnecessary questionnaires
Section 4.2	Subjects allowed to continue stool diary longer to enable 11 days of data collection prior to randomization	Several subjects needed a few extra days to collect the required data, especially those with cognitive impairment
Section 4.2, 4.3,4.4, 4.5, 4.6,	Combined SAPS-PD and hallucination questionnaire	To keep hallucination related questions together
Section 4.1, 4.2, 4.3, 4.4, 4.5	L-Dopa sub-study related language clarified	Was confusing to coordinators
Section 4.1, Table 1 footnote, Appendix 2	Language relating to orthostatic blood pressure measurements clarified.	
Section 3.3, 4.0, 4.1	UPDRS certification requirement removed	Covid is making it difficult to recertify coordinators every 6 months

CONFIDENTIALITY STATEMENT

This study will be performed in accordance with ethical principles that have their origin in the Declaration of Helsinki and conducted in adherence to the study Protocol, Good Clinical Practices as defined in Title 21 of the US Code of Federal Regulations Parts 11, 50, 54, 56, and 312, as well as ICH GCP consolidated guidelines (E6) and applicable regulatory requirements.

This document is confidential and proprietary to Enterin, Inc. Acceptance of this document constitutes agreement by the recipient that no unpublished information contained herein will be reproduced, published, or otherwise disseminated or disclosed without prior written approval of Enterin, Inc., except that this document may be disclosed in any medium to appropriate clinical investigators, Institutional Review Boards, and others directly involved in the clinical investigation that is the subject of this information under the condition that they keep the information strictly confidential.

BDI-II	Beck Depression Inventory II
CNS	Central nervous system
CRO	Contract Research Organization
CSBM	Complete spontaneous bowel movement, defined as a bowel movement (BM) that did not occur within 24 hours following use of rescue medication, where the subject felt that he/she had no more stool to pass and was completely emptied out.
C-SSRS	Columbia-Suicide Severity Rating Scale
CTCAE	Common Terminology Criteria for Adverse Events
DLT	Dose Limiting Tolerability
DSMB	Data Safety and Monitoring Board
eCRF	Electronic Case Report Form
ECG	Electrocardiogram
eCRF	Electronic Case Report Form
ENS	Enteric nervous system
EoS	End of study
EoT	End of Treatment
FDA	Food and Drug Administration
FSH	Follicle-stimulating hormone
GCP	Good Clinical Practice
GI	Gastrointestinal
ICF	Informed Consent Form
IRB	Institutional Review Board
IRT	Interactive Response Technology. IRT includes Interactive Voice Response system and Interactive Web Response system
IWRS	Interactive Web Response System
L-Dopa	Levodopa
LFT	Liver function test

CONFIDENTIAL**19April21_7.0**

MDS-UPDRS	Movement Disorder Society's Unified Parkinson's Disease Rating Scale
mITT	Modified Intent-to-treat
MMSE	Mini Mental State Examination
MTD	Maximum Tolerable Dose
PAC-QOL	Patient Assessment of Constipation - Quality of Life
PAC-SYM	Patient Assessment of Constipation Symptoms
PD	Parkinson's Disease
PDSS	Parkinson's Disease Sleep Scale
PFS	Parkinson's Disease Fatigue Scale
RBDQ	REM Sleep Behavior Disorder Questionnaire
REM	Rapid eye movement
SAE	Serious Adverse Event
SAPS-PD	Scale for Assessment of Positive Symptoms – Parkinson's Disease
SBM	Spontaneous bowel movement, defined as any bowel movement (BM) that did not occur within 24 hours following use of rescue medication
TEAE	Treatment Emergent Adverse Event
ULN	Upper Limit of Normal
UM-PDHQ	University of Miami Parkinson's Disease Hallucination Questionnaire
UPDRS	Unified Parkinson's Disease Rating Scale
WHO	World Health Organization

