- Dizziness defined as lightheadedness or fainting on rising from lying to sitting or standing that limits instrumental ADL and severe enough to indicate non-urgent medical intervention within 24 hours of taking study medication/placebo.

It is anticipated that all subjects receiving active treatment will exhibit a prokinetic effect at a dose lower than DLT.

Efficacy:

The primary efficacy objective will be evaluation of the efficacy of repeated daily doses of ENT-01 for up to 25 days in improving the CSBM rate.

A CSBM is a bowel movement where the subject indicated that he/she was “done for the day”, that he/she had “no more poop left to pass” and the bowel movement was not a1 or 2 on the Bristol stool scale and did not occur within 24 hours after taking rescue medication. For each subject, the Fixed Dose period begins on the first day of the subject’s prokinetic dose, (or the highest dose at which the subject did not have a DLT), following the incremental dosing algorithm defined in Section 4.2, Visit 2: Randomization (Study Day1).

Primary Efficacy Endpoint: The primary efficacy endpoint is the change from baseline in the weekly CSBM rate during the Fixed Dose period. Baseline is defined as the weekly CSBM rate during the 2-week screening period. The fixed dose response will be obtained as the weekly CSBM rate during the Fixed Dose period. For each subject, the Fixed Dose period begins on the first day of the subject’s prokinetic dose, (or the highest dose at which the subject did not have a DLT), following the incremental dosing algorithm defined in section 4.2 Visit 2: Randomization (Study Day 0, treatment begins the following day at home).

The frequency of CSBMs will be determined via a web-based electronic diary where the passage of a bowel movement or absence thereof will be recorded daily throughout the study by the subject.

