3.2 Secondary Objectives and Endpoints

The secondary objectives of the study are:

1. To determine if the correct starting dose (75 mg or 150 mg) can be predicted from the baseline weekly CSBM rate
2. To collect information on the effect of ENT-01 on CSBM, SBM, ease of passage,

consistency, suppository/enema use and subjective bowel function and quality of life (QOL)

Secondary efficacy endpoints will include the following:

- Frequency of dose adjustments in the Dose Adjustment period: The number of dose adjustments a subject has from the initial starting dose to the subject's fixed dose.
- Prokinetic bowel response during the Fixed Dose period: A prokinetic response is defined as a weekly CSBM rate increase of 1 or more compared to baseline or an absolute rate of 3 or more CSBMs per week.
- Change from baseline in the weekly SBM rate during the Fixed Dose period: An SBM is a bowel movement which did not occur within 24 hours after taking rescue medication.
- SBM bowel response to ENT-01 during the Fixed Dose period: An SBM bowel response is defined as a weekly SBM rate increase of 1 or more compared to baseline or an absolute rate of 3 or more SBMs per week.
- Change from baseline in stool ease of passage during the Fixed Dose period: Stool ease of passage is rated on a 1-7 ordinal point scale (see [APPENDIX 5](#)). A subject's ease of passage score for a given time period is the average of the ease of passage scores associated with SBMs during that time period.
- Change from baseline in stool consistency during the Fixed Dose period: Stool consistency is measured using the 7-point Bristol Stool Chart (see [APPENDIX 6](#)). A subject's stool consistency score for a given time period is the average of the stool consistency scores associated with SBMs during that time period.
- Change from baseline in suppository/enema use during the Fixed Dose period: Suppository/enema use is measured as a weekly average during the Fixed Dose period. This is captured in the subject stool diary.
- Time to first CSBM in the Fixed Dose period: Time to first CSBM in the Fixed Dose period is defined as the time from the subject taking the first dose of study medication in the Fixed Dose period until the subject has aCSBM.

- Time to first SBM in the Fixed Dose period: Time to first SBM in the Fixed Dose period is defined as the time from the subject taking the first dose of study medication in the Fixed Dose period until the subject has an SBM.

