5.7 Concomitant and Prohibited Medication

- Preventive laxatives will be discontinued during the screening period. This will include all prescription laxatives, over the counter laxatives and dietary supplements. Throughout the study, subjects will be allowed to take constipation rescue medication on demand, and only if they have not had a bowel movement in three consecutive days. Rescue medications will be recorded in the electronic daily diary every time a laxative is used. Bowel movement produced within 24 hours of rescue medication or accidental self-prescribed laxative use will not be counted as either spontaneous bowel movement or complete spontaneous bowel movement.
- Proton pump inhibitors and antacids will be discontinued at the end of the screening period and reinstated during the wash-out period.
- Barbiturates, and opiates will be discontinued at the end of the screening period and 2-3 days before dosing and reinstated during the wash-out period. All medications shall be reviewed and dis/approved by the investigator on a case-by-case basis.
- Selective serotonin reuptake inhibitor (SSRI), SNRI, tricyclic antidepressant, anti-cholinergic, anti-histaminergic and anti-psychotic agents are permissible at stable doses.
- Dopamine agonists and amantadine will be allowed if on a stable dose for at least 2 weeks preceding the study.
- Deep brain stimulation is allowed if present for more than 6 months and at stable stimulation parameters.

Subgroup Analyses

[figure not shown]
Subjects will be analyzed overall by their randomized treatment assignment (i.e., active versus placebo). Subgroup analyses will also be performed by a subject's baseline CSBM rate (i.e., 0-0.9, or 1.0-3.0). The primary efficacy endpoint and key secondary, exploratory and safety endpoints will be summarized by these subgroups. Additional subgroup analyses may be defined in the statistical analysis plan (SAP).

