4.6.1 Derivation of Weekly CSBM and SBM Rates

There are 4 CSBM Definitions, each of which are based on the set of questions from the patient's daily diary. The rates from each of the CSBM definitions will be presented. Note: since the assessments are different between the 2 cohorts the definitions are different.

CSBM Definition 1:

A CSBM is a BM which meets each of the following 3 criteria.

For the 1st Cohort of patients:

- 1) For this BM the patient responded "No rescue medication used" to the query "Have you used rescue medication within 24 hours prior to this bowel movement?"
- 2) For this BM the patient responded
 - "Yes" to the query "Did you feel like you completely emptied your bowels?"
OR
 - "No" to the query "Did you feel like you completely emptied your bowels?" but the BSFS Ease of Passage score is 6 or 7.
- 3) The bowel movement has a BSFS Ease of Passage score of 3 or greater (or missing).

For the 2nd Cohort of patient:

- 1) No rescue mediation was taken within 24 hours of the Bowel Movement (note: the date and time of the bowel movements and rescue medication (i.e., laxative) use are included in the subjects daily diary data).
- 2) For this BM the patient responded :
 - “No” to the query “Do you feel like you have more poop left to pass?”OR
 - “Yes” to the query “Do you feel like you have more poop left to pass?” and the BSFS Ease of Passage score is 6 or 7.
- 3) The bowel movement has a BSFS Ease of Passage score of 3 or greater (or missing).

CSBM Definition 2:

The 2nd CSBM definition removes the BSFS criteria from the CSBM definition. A CSBM is a BM which meets each of the following 2 criteria

For the 1st Cohort of patients:

- 1) For this BM the patient responded “No rescue medication used” to the query “Have you used rescue medication within 24 hours prior to this bowel movement?”
- 2) For this BM the patient responded “Yes” to the query “Did you feel like you completely emptied your bowels?”

For the 2nd Cohort of patient:

- 1) No rescue mediation was taken within 24 hours of the Bowel Movement (note: the date and time of the bowel movements and rescue medication (i.e., laxative) use are included in the subjects daily diary data).
- 2) For this BM the patient responded “No” to the query “Do you feel like you have more poop left to pass?”

CSBM Definition 3:

The 3rd CSBM definition broadens the definition of a CSBM for the 2nd cohort. A CSBM is a BM which meets each of the following 2 criteria

For the 1st Cohort of patients:

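### Protocol 5.7 also bars stools after self-prescribed laxatives, but the endpoint definitions, the SAP's first-cohort CSBM criteria and its SBM rule test rescue medication only

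*Protocol*

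**What the plan says.** Protocol 5.7 sets a counting rule with two triggers: "Bowel movement produced within 24 hours of rescue medication or accidental self-prescribed laxative use will not be counted as either spontaneous bowel movement", and it applies the same rule to complete spontaneous movements.

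The definitions that feed the endpoints have one trigger. In the Protocol's list of abbreviations, CSBM is "Complete spontaneous bowel movement, defined as a bowel movement (BM) that did not occur within 24 hours following use of rescue medication", with completeness added, and SBM is worded in the same way. Protocol 3.1, which defines the primary endpoint, requires that the stool "did not occur within 24 hours after taking rescue medication". Protocol 3.2 says "An SBM is a bowel movement which did not occur within 24 hours after taking rescue medication". Protocol Section 4 describes rescue medication as suppositories and enemas supplied to the subject.

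SAP 4.6.1 puts this into practice in three ways:

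- **First-cohort CSBMs**, all four definitions: the patient must have answered that none was used when asked "Have you used rescue medication within 24 hours prior to this bowel movement".
- **Second-cohort CSBMs**, all four definitions: "No rescue mediation was taken within 24 hours of the Bowel Movement" (the misspelling is the SAP's). A note adds that the timing comes from diary data and equates rescue medication with laxative use.
- **SBMs**: one rule with no split by cohort, resting on the same rescue-medication question used for the first cohort.

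SAP 4.6.2 scores stool consistency and ease of passage on SBMs only. SAP Section 5 declares no departures from the protocol's analyses.

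**The concern.** The counting rule decides which stools enter the primary endpoint and the stool-based secondary endpoints. Subjects are constipated and have been told to stop their laxatives, and Protocol 5.7 itself foresees that some will take one anyway. If the programmer follows the SAP and not 5.7, a laxative-induced stool can be recorded as spontaneous.

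The rule also differs between cohorts for CSBMs and, within the second cohort, between CSBMs and SBMs. That inconsistency affects the primary endpoint through the first cohort. In both cohorts it affects the SBM rate, SBM response, time to first SBM, ease of passage and consistency.

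**Working it through.** No stated power or sample-size figure depends on this point, so there is nothing to reproduce. The check is a comparison of the rules, followed by arithmetic for scale.

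**The rules side by side**

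| Place | Applies to | What disqualifies a stool |
|---|---|---|
| Protocol 5.7 | SBM and CSBM | Rescue medication or self-prescribed laxative |
| Protocol list of abbreviations | SBM and CSBM | Rescue medication |
| Protocol 3.1 | CSBM (primary endpoint) | Rescue medication |
| Protocol 3.2 | SBM | Rescue medication |
| SAP 4.6.1, first cohort | CSBM | Patient's answer about rescue medication |
| SAP 4.6.1, second cohort | CSBM | Timed diary record, rescue equated with laxative |
| SAP 4.6.1, no cohort split | SBM | Patient's answer about rescue medication |

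**One stool traced through them.** Suppose a subject takes an oral laxative independently, records it, and next morning passes a complete stool of normal form.

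- Protocol 5.7: neither an SBM nor a CSBM.
- SAP, first cohort: the subject can truthfully answer that no rescue medication was used, so the stool could count as both.
- SAP, second cohort: rejected as a CSBM if the diary gloss covers any laxative, yet accepted as an SBM if the rescue question is applied. It would then be scored for ease of passage and consistency.

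SAP 4.6.1 also says the assessments differ between the cohorts, yet its SBM rule quotes the first-cohort question for everyone. The documents do not show whether second-cohort subjects were asked it.

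**Scale for one subject.** The SAP formula is weekly rate = 7 × stools ÷ days in the period. The assumed treatment difference in Protocol 9.2.5 is 3.55 − 1.28 = 2.27 per week. One miscounted stool adds:

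| Fixed Dose window | Added weekly rate | Share of 2.27 |
|---|---|---|
| 7 days | 7 × 1/7 = 1.00 | 44% |
| 14 days | 7 × 1/14 = 0.50 | 22% |
| 25 days | 7 × 1/25 = 0.28 | 12% |

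These are shifts for one subject, not for a group mean. In the seven-day case the shift equals the increase of 1 per week that defines a prokinetic or SBM response. In a baseline of 14 days, one such stool adds 0.50 per week (0.64 with 11 days), which lowers the change from baseline.

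**Scale for a group.** The shift in an arm's mean is the share of subjects affected × counted laxative stools per week, less any matching shift at baseline. The documents give none of these. They do give approximate allocation: 54 active and 18 placebo in the first cohort, and 40 and 40 in the second. For CSBMs, a shift confined to the first cohort would be diluted on pooling to 18/58 = 0.31 of its size in the placebo arm and 54/94 = 0.57 in the active arm.

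**The case against.** The strongest reply is that 5.7 is itself an operative rule for both counts, and that the shorter definitions are incomplete restatements of it. Section 5.7 also uses the terms loosely, saying that rescue medication is recorded whenever a laxative is taken, so subjects may have understood rescue to include any laxative. The diary screens in Appendix 7 are not visible in the text available, nor are the instructions given to the first cohort. This stands to the extent that one can say only that such a stool could count, not that it did. It does not remove the need for a fix: the SAP governs the programming, it does not carry the laxative clause over, and Appendix 7 names laxative and rescue use as separate items.

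A reader might infer that laxative-induced stools enter the primary endpoint generally. The documents do not support that. All four second-cohort CSBM definitions use timed diary data that the SAP equates with laxative use, and Protocol 4.1 requires laxative use to be entered in the diary.

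A reader might also infer that the treatment difference is diluted because placebo subjects would self-medicate more. No rate is given for either arm. Miscounting at baseline works the other way. If self-medication were equal across arms, the 3:1 allocation would place more of the first-cohort miscounting in the pooled active mean (0.57 against 0.31), and the primary ANCOVA has no cohort term.

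Repeated laxative use might be judged a major deviation and remove the subject from the Efficacy Evaluable Population. That safeguard is discretionary and acts on subjects, not stools, and SAP 4.6.3 bases its primary analysis on the Fixed Dose Population.

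Finally, the second-cohort wording does not say that the 24 hours precede the stool. Read literally, it could drop a stool passed before rescue. The surrounding definitions make the intent clear, so this is a minor drafting point.

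**Conclusion.** The point holds in a limited form. Protocol 5.7 excludes more stools than the Protocol's own definitions, the SAP's first-cohort CSBM criteria or its single SBM rule. As written, a stool after a self-prescribed laxative could count as a CSBM in the first cohort and as an SBM in either cohort, with ease of passage and consistency following. In the second cohort one stool could fail as a CSBM and pass as an SBM.

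The size and direction of any bias cannot be computed from the documents. The per-subject figure of 1.0 per week assumes one miscounted stool and a seven-day window. The reading that second-cohort CSBMs are protected assumes that the diary gloss covers every recorded laxative, which the SAP should state outright. The gap is worth closing because the counting rule feeds the primary endpoint and the sponsor has already written the rule needed to close it.

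**What to change.** Reconcile the passages by applying the existing 5.7 counting rule in the Protocol's list of abbreviations, Protocol 3.1 and 3.2, and SAP 4.6.1, for SBMs as well as CSBMs. This concerns which stools are counted; it takes no view on which medications subjects should be allowed.

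- **Second cohort:** derive both SBMs and CSBMs from the timed laxative and rescue diary. State that it covers any laxative and that the interval is the 24 hours before the stool.
- **First cohort:** an unblinded interim analysis has already been done on these subjects, so changing their main derivation now would be a change made after unblinding. Keep the per-stool question as the main derivation. Add a pre-specified sensitivity analysis that excludes stools within 24 hours of any laxative found in the available diary or concomitant-medication records, and give a calendar-day convention for entries without times.
- **Timing:** settle both before the second cohort is unblinded.

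The cost is revised wording and a small data merge. The documents do not show a timed laxative log for the first cohort, so its sensitivity analysis may be approximate.
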